## Analysis of safety and tolerability endpoints

The safety set is used to perform all safety analyses. Baseline is defined as the last value prior to dosing. Change from baseline will be calculated for all continuous safety parameters.

### Adverse events

The AE coding dictionary for this study will be Medical Dictionary for Regulatory Activities (MedDRA). It will be used to summarize AEs by primary system organ class (SOC) and preferred term (PT).

All adverse events will be displayed in listings.

A treatment-emergent adverse event (TEAE) is defined as an adverse event observed after starting administration of the specific treatment. If a subject experience an event both prior to and after

starting administration of a treatment, the event will be considered a TEAE (of the treatment) only if it has worsened in severity (i.e., it is reported with a new start date) after starting administration of the specific treatment, and prior to the start of another treatment, if any. All TEAEs collected during the investigational period will be summarized.

The number of treatment emergent AEs will be summarized by:

- 1. treatment, MedDRA SOC and PT;
- 2. treatment, MedDRA SOC, PT and severity;
- 3. treatment, MedDRA SOC, PT and drug relatedness.

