#### Physical examination

Physical examination (i.e., inspection, percussion, palpation, and auscultation) is performed during the course of the study. Clinically relevant findings that are present prior to study drug initiation must be recorded with the subject's Medical History. Clinically relevant findings found after study drug initiation and meeting the definition of an AE (new AE or worsening of previously existing condition) must be recorded.

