#### Capsaicin 1% application

Capsaicin application and related tests (heat pain test on capsaicin-treated skin and control skin on contralateral arm, and Von Frey test) will only be performed for subjects found eligible at screening (i.e., not to be allergic and/or tolerable to the capsaicin solution). Subjects allergic and/or intolerable to the capsaicin solution may participate in the trial; no capsaicin-related measurements will be performed for them.

The capsaicin 1% model is included as a model for heat and mechanical allodynia. Capsaicin is applied during screening procedures, to evaluate whether subjects are allergic to the solution, and applied 60 minutes prior to study drug administration. A 3x3 cm surface on the dominant volar forearm is used as application site; the non-dominant volar forearm serves as a non-stimulated control. At 30 minutes post-application, abundant solution is wiped off towards the centre of the application site, if necessary. Immediately after, and subsequently at given time points, Von Frey hair filament assessments and heat pain tests are performed on the 3x3 cm area.

Capsaicin application and related tests (heat pain test on capsaicin-treated skin and control skin on contralateral arm, and Von Frey test) will only be performed for subjects found eligible at screening (i.e., not to be allergic and/or tolerable to the capsaicin solution). Subjects allergic and/or intolerable to the capsaicin solution may participate in the trial; no capsaicin-related measurements will be performed for them.

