#### 2.12 SAFETY REPORTING

#### 2.12.1 Definitions

### Adverse events (AEs)

Adverse events are defined as any untoward medical occurrence in a subject to whom a medicinal product is administered, and which does not necessarily have a causal relationship with this treatment.

The intensity/severity of clinical AEs is graded on a 3-point scale as defined below:

- Mild: discomfort noticed but no disruption of normal daily activity,
- Moderate: discomfort sufficient to reduce or affect normal daily activity,
- Severe: inability to work or perform daily activity.

For each AE the causal relationship to the drug will be judged by the investigator as defined below:

- · Probably related,
- Possibly related,
- Not related.

The chronicity of the AE will be classified by the investigator on a 3-item scale as defined below:

- Single occasion: single event with limited duration,
- Intermittent: several episodes of an event, each of limited duration,
- Persistent: event which remained indefinitely.

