### 2.13.2 Analysis sets

Data of all subjects participating in the study will be included in the analyses if the data can meaningfully contribute to the objectives of the study.

Safety set

The safety population will be defined as all subjects who were validated (randomised) and received at least 1 dose of study treatment.

Pharmacokinetic analysis set

The PK analysis population is defined as all subjects who were validated (randomised), received at least one dose of study treatment, and have at least one measurable drug concentration in samples collected.

Pharmacodynamic analysis set

The analysis population for pharmacodynamics is defined as all subjects who were validated (randomised), received at least one dose of study treatment, and have at least one post-baseline assessment of the parameter been analysed.

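### The TEAE rule charges a pre-dose capsaicin reaction in period 2 to the period 1 regimen, and leaves the same reaction in period 1 out of the summary tables

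*Protocol*

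**What the plan says.** **Counting rule.** Section 2.13.6 (Adverse events) of the protocol gives the basic definition: "A treatment-emergent adverse event (TEAE) is defined as an adverse event observed after starting administration of the specific treatment". For an event seen both before and after dosing, "the event will be considered a TEAE (of the treatment) only if it has worsened in severity", and the worsening must fall "after starting administration of the specific treatment, and prior to the start of another treatment, if any". TEAEs are summarised by treatment. All AEs, treatment-emergent or not, go into listings.

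**Capsaicin.** Section 2.10.3 says: "Capsaicin is applied during screening procedures, to evaluate whether subjects are allergic to the solution, and applied 60 minutes prior to study drug administration". Section 2.7.4 classes capsaicin 1% as an auxiliary medicinal product and justifies it as a product for which no market-approved form would serve. The Synopsis expects transient irritation, redness and burning that usually settle within one or two days.

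**What counts as an AE.** Section 2.12.1 defines it as "any untoward medical occurrence in a subject to whom a medicinal product is administered", with no need for a causal link. The investigator makes one causality judgement per AE, and it concerns the drug.

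**Who is analysed.** Under section 2.13.2 the safety set is "all subjects who were validated (randomised) and received at least 1 dose of study treatment".

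**When AEs are collected.** Table 2 has (S)AEs collected at each visit throughout the study. In Table 1 as it can be read here, the (S)AE row seems to have no screening entry, although the concomitant medication row has one.

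**The concern.** The TEAE clock starts at study drug, but each treatment period starts one hour earlier with another medicinal product that is expected to cause skin reactions. In a parallel-group trial such events would simply fall before treatment. In a cross-over, the pre-dose hour of period 2 also lies after the period 1 dose. Nothing in the rule separates the two, so whether a procedure reaction is counted, and under which regimen, depends on the period in which it occurs.

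Tolerability of the regimens is a secondary objective, and TEAEs are its endpoint. With 24 subjects, a few events in the wrong column are visible in a TEAE table.

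**Working it through.** The protocol states no AE rate or count on this point, so there is no figure of its own to reproduce. The check places each capsaicin application on the timeline and applies the wording of section 2.13.6 by time of onset.

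**Inputs**
- TEAE start: start of the specific study treatment, 0 h of each period (2.13.6).
- TEAE end: none in the basic definition. The words "prior to the start of another treatment, if any" stand only in the sentence on events that worsen.
- Capsaicin: screening, then 60 minutes before dosing in each period (2.10.3).
- Gap between periods: at least 7 days (Synopsis, Trial Design).
- Subjects: 24 (2.5.2). Regimens: two (Synopsis and 2.7.1). Sections 2.5.2 and 2.5.3 still speak of four periods; the two-regimen layout is used here.

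**Classification**
1. *Screening application.* Onset precedes all study treatment, so the event is not a TEAE and is in no summary table. If the person is never dosed, he or she is also outside the safety set.
2. *Period 1, onset between -60 min and 0 h.* Not a TEAE unless it worsens after dosing. If it worsens, it is a TEAE of the period 1 regimen.
3. *Period 2, onset between -60 min and 0 h.* After the start of the period 1 regimen and before the start of the period 2 regimen. It is a TEAE of the period 1 regimen, at least 7 days after that dose. If it worsens after the period 2 dose, it is also a TEAE of the period 2 regimen.
4. *Either period, first observed after 0 h.* A TEAE of the current regimen. With capsaicin applied one hour earlier and effects lasting one to two days, this route may be common.

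Case 3 does not depend on how the end limit is read. Whether the limit applies to every TEAE or only to worsening ones, the hour before the period 2 dose is still inside the period 1 window.

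**Size**

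Suppose all 24 subjects are capsaicin-eligible and complete both periods, and the two sequences are balanced (the sequence ratio is not stated). Then 24 / 2 = 12 subjects have each regimen in period 1. Let q be the proportion with a recorded AE starting in the pre-dose hour of period 2, counted once per subject:

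- misplaced events per regimen = 12 × q;
- q = 0 gives 0, and q = 1 gives 12 × 1 = 12;
- over both regimens the ceiling is 2 × 12 = 24.

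The documents contain nothing that fixes q. Because each regimen receives 12q in expectation, the expected difference between regimens is 12q - 12q = 0. Both counts are raised and noise is added.

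**The case against.** **All AEs are listed.** A reader might infer that capsaicin reactions go unreported. The documents do not support that. Section 2.13.6 lists every AE, and Table 2 has (S)AEs collected at each visit. Only the summary tables are affected, and leaving out events before treatment is the ordinary meaning of treatment-emergent. This stands, and it limits the point to tabulation.

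**The Medical History rule is narrow.** Section 2.10.3 says of the physical examination: "Clinically relevant findings that are present prior to study drug initiation must be recorded" with the medical history. A reader might take this to divert capsaicin reactions away from AE recording. It covers examination findings only, so it does not show that.

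**Table 1 is weak evidence.** The missing screening entry is read from a table broken in extraction. It supports a request to reconcile, not a finding that screening AEs go uncollected.

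**The effect is small.** Subjects allergic or intolerant to capsaicin at screening are not re-exposed, and expected transient irritation may not be recorded as an AE at all. TEAEs are also tabulated by relatedness, so an application-site reaction marked as not related could be recognised there. The study is exploratory. All of this stands and keeps the point minor.

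**The window end could be left to the SAP.** This does not remove the point. The protocol already fixes the counting rule, and that rule as written puts the period 2 event in the wrong column.

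**A dosed safety set is conventional.** Agreed. The definition of the safety set is not itself an error.

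**Conclusion.** The point holds as a minor defect in a stated rule. Taken literally, section 2.13.6 assigns a capsaicin reaction in the pre-dose hour of period 2 to the regimen of the previous period, and leaves the identical period 1 event out of the summaries unless it worsens. Reactions first seen or worsening after 0 h enter the current regimen's column, and the single causality judgement does not separate capsaicin from study drug.

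The size cannot be derived from the protocol. The ceiling of 12 per regimen needs full capsaicin eligibility, full completion, balanced sequences, and a recorded pre-dose reaction in every subject. The true number is probably well below that, since only subjects who tolerated capsaicin at screening are exposed again.

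A reader might also infer that the comparison between regimens is biased. With balanced sequences it is not, in expectation: both regimens' counts are inflated alike and become noisier.

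**What to change.** - In section 2.13.6, give each regimen's TEAE window an explicit start and end, with the end no later than the capsaicin application of the next period.
- Tabulate events with onset between capsaicin application and study drug separately, in neither regimen column.
- In section 2.12.1, record relatedness to capsaicin separately from relatedness to study drug. Without this, capsaicin reactions first seen after dosing stay indistinguishable in the regimen columns.
- Reconcile the (S)AE row of Table 1 with Table 2, so that AE collection clearly covers the screening application.

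The cost is a few sentences, one extra relatedness field, one small table and slightly more AE recording. No dose or assessment time changes.

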#### **Objectives**

The primary objectives are:

[figure not shown]
 To evaluate the analgesic effects of morphine, nortriptyline and the two drugs as combination using PainCart®

The secondary objectives are:

- To evaluate the effects on central nervous system (CNS) functioning of morphine, nortriptyline and the two drugs as combination as measured using NeuroCart®
- To compare the tolerability of morphine alone, nortriptyline alone and the two drugs when given together
- To evaluate the blood pharmacokinetics of morphine, nortriptyline and the two drugs as combination

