#### Replacement policy

Subjects withdrawing, or being withdrawn, for reasons other than (possibly or probably related) AEs or any other tolerability issues with the treatment can be replaced at the discretion of the investigator. The rationale for replacement must be clearly documented in the source (e.g., note in Promasys, Filenotes, etc.)

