# 2.13.3 Participant demographics and other baseline characteristics

Subject disposition will be listed by subject.

The following subject data will be summarized:

- number and percentage of subjects screened,
- number and percentage of subjects enrolled,
- number and percentage of subjects completed,
- number and percentage of subjects included in safety population.

Demographics and baseline variables

Continuous demographic variables (e.g., age, height, weight, BMI) will be summarized by descriptive statistics (n, mean, SD, median, Min, Max). Qualitative demographic characteristics (sex, race/ethnicity) will be summarized by counts and percentages.

Medical history

Medical history will only be listed.

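### Adverse events are to be summarised as counts of events only, with no number or percentage of subjects affected among those who received each treatment

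*Protocol*

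**What the plan says.** Section 2.13.6 of the protocol, under Adverse events, fixes the summary: "The number of treatment emergent AEs will be summarized by" treatment, SOC and PT; then by "treatment, MedDRA SOC, PT and severity"; then by treatment, SOC, PT and drug relatedness. The measure in all three tables is a number of events. The same section adds: "All adverse events will be displayed in listings".

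The Synopsis sets a comparative secondary objective for these tables to serve: "To compare the tolerability of morphine alone, nortriptyline alone and the two drugs when given together". Table 2 names treatment-emergent (serious) adverse events as an endpoint for safety and tolerability.

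Two other provisions bear on the denominator. Under the Replacement policy in section 2.11.3, subjects who withdraw "for reasons other than (possibly or probably related) AEs or any other tolerability issues with the treatment can be replaced" at the investigator's discretion; no replacement is provided for the rest. The safety set in section 2.13.2 takes every randomised subject with at least one dose of study treatment and is not defined by treatment received.

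Elsewhere the protocol does plan subject counts. The disposition summary, for example, includes the "number and percentage of subjects included in safety population".

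**The concern.** A tolerability comparison within subjects asks how many patients were affected on each regimen. A total of events does not answer that, because it multiplies two things together: how many subjects were affected, and how many records each contributed. It also carries no information on how many subjects were exposed.

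The second gap matters in a crossover with selective replacement. A subject who leaves after the first period because of a related event contributes nothing to the other regimen and falls outside the replacement provision. The numbers exposed can therefore differ between regimens for a reason linked to tolerability itself, and a raw count would not show it.

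At stake is whether a stated secondary objective can be read from the planned tables. A difference in counts could not be taken as a difference in patients harmed, and equal counts could not be taken as equal tolerability.

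**Working it through.** The protocol states no figure on this point, so there is none to reproduce. The check is of the text, followed by arithmetic on assumed inputs.

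**Inputs from the protocol**
- Planned subjects: 24 (section 2.5.2).
- AE measure: number of treatment-emergent events (section 2.13.6).
- Replacement: not provided for withdrawals due to related events or tolerability (section 2.11.3).

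**Inputs assumed, because the protocol gives none**
- True incidence of 50% on both regimens.
- 1 or 2 records per affected subject.
- m = 0, 1, 2 or 4 subjects who miss one regimen, all of them the same regimen.

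**Step 1: repeat records**

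Events = subjects affected × records per subject.
- One record each: 12 × 1 = 12 events; incidence 12/24 = 50%.
- Two records each: 12 × 2 = 24 events; incidence 12/24 = 50%.

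The count doubles while the proportion of subjects affected is unchanged. This shows only what a count cannot separate. It is not evidence that the comparison between these two regimens will be wrong.

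**Step 2: unequal exposure**

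Expected events = subjects exposed × incidence, with one record per affected subject. The regimen that all 24 receive has 24 × 0.50 = 12. The other has (24 − m) × 0.50.

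| m | Exposed | Expected events | Ratio to 12 | Incidence per exposed subject |
|---|---|---|---|---|
| 0 | 24 | 12 | 1.00 | 50% |
| 1 | 23 | 11.5 | 0.96 | 50% |
| 2 | 22 | 11 | 0.92 | 50% |
| 4 | 20 | 10 | 0.83 | 50% |

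The ratio is (24 − m)/24, so it does not depend on the assumed 50%. The count falls by about 4% at m = 1 and 17% at m = 4. If the missed periods were spread over both regimens, the net effect would be smaller.

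**Step 3: which denominator**

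Adding a percentage does not settle the matter unless its denominator is stated. With m = 4, 10 affected subjects over a safety set of 24 gives 10/24 = 42%; over the 20 who received that regimen it gives 10/20 = 50%, the assumed true value. Because the safety set is not defined per treatment, the wording has to name the denominator.

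**The case against.** The strongest reply is that the layout of adverse event tables is usually left to the statistical analysis plan, which is not at hand, and that section 2.13.6 does not exclude subject counts. Every event is listed, so subject incidence can be derived without new data. The study is also exploratory, with no formal hypothesis (Inferential methods, section 2.13.5). Much of this stands: it makes the point minor, and it means that the protocol cannot be said to rule out incidence. It does not remove the point, because the protocol is not silent. It names a measure, and that measure is incomplete for its own objective. A listing from which incidence could be derived is not a planned summary of it.

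A reader might infer more than the documents support in three ways.
- **The two morphine boluses distort the contrast.** Both regimens receive 3 mg at 2 h and 7 mg at 5 h (section 2.7.1), so the boluses by themselves favour neither. If recurrence did differ by regimen, that would itself be tolerability information.
- **Every recurrence is a further event.** The chronicity scale in section 2.12.1 has a class "Intermittent: several episodes of an event, each of limited duration", which may hold several episodes in one record. The clause that counts an event if "it has worsened in severity (i.e., it is reported with a new start date" decides whether an event already present before a treatment becomes emergent on it. It does not settle how recurrence within a period is recorded.
- **The counts will be biased in a known direction or by a large amount.** No event or dropout rate is given, and the exposure effect is small unless several subjects leave between periods.

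**Conclusion.** The point holds as a minor reporting correction. The protocol fixes the adverse event summary as a count of events by treatment, with no subjects affected and no per-treatment denominator, while it sets a tolerability comparison between regimens and allows the numbers exposed to differ for tolerability reasons. Followed as written, the tables mix incidence with repeat records and ignore exposure.

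The size and direction of any distortion are unknown. The 4% to 17% range rests on 1 to 4 of 24 subjects missing the same regimen, which is an assumption; the effect of repeat records depends on recording conventions that the protocol does not give. The documents do not show that the comparison will be misstated, only that the planned tables could not reveal whether it is. Nothing here touches clinical management.

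**What to change.** In section 2.13.6, Adverse events, replace the sentence that introduces the three tables with wording to this effect: the number and percentage of subjects with at least one treatment-emergent adverse event (denominator: subjects who received that treatment), together with the number of events, will be summarised by treatment, SOC and PT, and likewise by severity and by drug relatedness; each subject is counted once per PT, at the highest severity or relatedness.

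The cost is a change of wording and somewhat longer tables. No new data, procedures or visits are needed. The event counts stay, so nothing now planned is lost.

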### Vital signs

At each time point, absolute values and change from baseline of supine blood pressure and pulse rate will be summarized with n, mean, SD, SEM, median, Min, and Max values. The number of available observations and out-of-range values (absolute and in percentage) will be presented. Values outside the reference range will be flagged in the listing. 'H' and 'L', denoting values above or below the investigator reference range (when present), will flag out-of-range results.

